9.1 Determination of Sample Size

A subject is determined to reach the primary endpoint “stabilization or improvement in clinical status defined as maintenance or improvement by one category on a 6-category clinical status scale on Day 7” if the clinical status category on Day 7 is not worse than the clinical status category at Baseline (Day 1 prior to IMP infusion).

The study is determined to be successful if the proportion of subjects randomized to the IVIG group who reach the primary endpoint is significantly greater than the proportion of subjects randomized to the placebo group who reach the primary endpoint.

High-dose IVIG is used as a therapeutic option for severe-type COVID-19 (37) and given the severity of the population in our study as compared to the reference study, we assume 80% of subjects in the IVIG group and 60% of subjects in the placebo group will meet the primary endpoint.

With overall two-sided significance level of 0.05 when testing the difference in proportions between two treatment groups using normality approximation, 176 subjects (n=88 for each treatment group) will provide statistical power of at least 80%. Assuming a drop-out rate of 15% from Baseline (Day 1) relative to the efficacy assessment date at Day 7 after first dose for both groups, a final sample size of 208 (n=104 for each treatment group) is sufficient to maintain the minimum statistical power as 80%.

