##### **4.1 Missing Data**

The latest patient status available prior to Day 7 will be used to determine clinical status in the absence of a clinical status assessment. If a death date is prior to Day 7, clinical status at Day 7 will be identified as a 6. Otherwise, if a subject's last status reflects that they were in the ICU and receiving ECMO and/or IMV, clinical status will be imputed as a 5. Otherwise, if a subject's last status reflects that they were in the ICU and not receiving ECMO and/or IMV, clinical status will be imputed as a 4. If the LOCF clinical status value for a patient is higher than these imputed values or if a subject status cannot be derived based on available information on ECMO, IMV, or ICU status, the last observation carried forward (LOCF)

will be used to impute patient values. Subjects with no post-baseline clinical status assessment, or prohibited medication use, on or prior to Day 7 will be imputed as failure.

An imputation analogous to the primary endpoint will be performed for the secondary endpoint of clinical status at Day 14.

For the secondary endpoint length of hospitalization, Subjects who are still hospitalized as of Day 33, subjects with missing end dates due to withdrawal, subjects with unusable end dates due to prohibited medication use, or those who died on/prior to Day 33 will be censored at Day 33. Discharge occurring on or after the start date of prohibited medication use will not be considered an event.

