Cumulative duration in ICU will be imputed similarly, unless a patient has a useable discharge date (e.g. not occurring prior to prohibited medication use); in this case, the ICU discharge date will be set to the hospital discharge date. If a subject's last assessment identifies that IMV was used (and has no usable end date), the date on which it is no longer used will be assumed Day 33 unless the subject is discharged from the hospital prior to Day 33. If this occurs, the hospital discharge date will be used. IMV end dates will be imputed similarly, assuming that IMV ceases at the time of ICU discharge. Hospitalization, ICU, and IMV end dates for subjects who died prior to Day 33 during these events (e.g. after ICU admission or IMV initiation) will result in assumed end dates of Day 33 for endpoint analyses, so long as prohibited medication was not administered. Any dates on or after the start date of prohibited medication use will be considered unusable for imputation purposes; ongoing hospitalization, ICU, or IMV at the time of medication use will default to extrapolation to Day 33.

For the key secondary endpoint involving severe progression (ECMO, IMV, and death), subjects who withdrew early from study prior to Day 33 without evidence of events will be treated as not having the event. Sensitivity analyses will be conducted (1) treating them as failures (having the event at their last study visit) and (2) excluding them from the analyses. An additional analysis of these endpoints will be provided, treating prohibited medication use prior to Day 33 as an event, as well as allowing for status (event or success) without regard to prohibited medication use.

The outcomes for safety assessment and for additional efficacy analysis as well as exploratory endpoints will not be imputed if data is missing.

Please also refer to the more detailed descriptions in sections 12 to 18 of this SAP for additional details on the handling of missing data for particular endpoints and analyses.

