## **13. Analysis of Primary Efficacy Endpoint**

The primary analysis will be based on the ITT Population. The null hypothesis of no difference in proportion of subjects who reach success (clinical status not worse than the clinical status category at Baseline at Day 7) in two treatment groups will be tested versus the alternative hypothesis that there is a difference between proportions of subjects who reach success in two groups. Hypothesis testing will be performed using Cochran-Mantel-Haenszel (CMH) stratified by age category ( $\leq 65$  versus  $> 65$ ) at a two-sided 0.05 significance level. The difference in proportions between two groups with standard deviation, and 95% Miettinen-Nurminen (1985) confidence interval (CI) will also be provided.

If the CMH fails the Mantel-Fleiss criteria (1980), a chi-squared test will be the basis of evaluation and unweighted asymptotic CIs for the difference in proportions will be used. If, when implementing a chi-squared test, an expected cell count  $< 5$ , Fisher's exact test will be used and exact (Santner-Snell, 1980) CIs will be provided.

For subjects with clinical status assessment at Baseline (Day 1), missing data at Day 7 will be imputed based on the method described in Section 4.1. Subjects with missing data at Baseline (Day 1) will be imputed as failure.

Subjects who use prohibited medication (medications being administered as part of other experimental studies or the use of experimental non-IVIG products, COVID-19 convalescent plasma, or interferons) on or before Day 7 will be counted as failure. Prohibited medications will be identified during blinded review described in Section 7.

Shifts from Baseline (Day 1) at Day 7 in terms of the 6-point clinical status scale will be reported (descriptive analysis).

The durability of the treatment effect will be reviewed based on the comparison of proportions who are stabilized or improved between treatment arms at Day 14, Day 21, and Day 33 in the final analysis. No formal hypothesis testing will be conducted for the Day 21 and Day 33 analyses and the descriptive comparison will be carried out based on the method applied for the primary analysis. Graphical representations of clinical status, and changes from baseline, over time will be presented by treatment group.

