## **17. Additional Efficacy Analysis**

The proportions of subjects stabilized or improved will be provided at Day 21 and Day 33 for both treatment arms. No hypothesis testing will be made for this analysis, but the difference of proportions will be presented, together with its standard error and the associated 95% confidence interval.

The proportions and frequencies of subjects' clinical status will be summarized over time. Frequencies and proportions of oxygen ventilator status will be also summarized over time. No hypothesis testing will be made for this analysis, but the difference of proportions will be presented, together with its standard error and associated 95% exact confidence interval.

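### SAP 4.1/17 and SAP 13 give different rules for missing Day 21 and Day 33 clinical status, and on one reading subjects who died can leave the durability comparison

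*SAP*

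**What the plan says.** SAP 4.1 (Missing Data) sets out how clinical status is filled in when there is no assessment. For death it says: "If a death date is prior to Day 7, clinical status at Day 7 will be identified as a 6". The next paragraph extends the scheme by analogy to Day 14 and to no later day. Protocol 9.2.5 likewise covers only Days 7 and 14. Near the end of SAP 4.1 comes the general exclusion: "The outcomes for safety assessment and for additional efficacy analysis as well as exploratory endpoints will not be imputed if data is missing".

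SAP 17 bears the title Additional Efficacy Analysis, and its first sentence reads: "The proportions of subjects stabilized or improved will be provided at Day 21 and Day 33 for both treatment arms". It asks for the difference, standard error and 95% confidence interval without a test. It states neither a denominator nor a rule for deaths.

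SAP 13, the primary-endpoint section, covers the same two days as a check on the durability of the treatment effect. There, "the descriptive comparison will be carried out based on the method applied for the primary analysis". The only imputation sentence in that section concerns Day 7.

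**The concern.** A subject who dies on Day 16 will normally have no clinical-status assessment at Day 21 or Day 33. At Days 7 and 14 the SAP treats this as an absent assessment and fills in category 6 from the death date. At Days 21 and 33 no such step is written, and Section 17 falls under the no-imputation sentence. A programmer who follows 4.1 and 17 literally could leave that subject out. One who follows 13 could count the same subject as a failure. Both could claim to have followed the SAP.

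At stake is the output the plan uses to show whether a Day 7 effect lasts. Death is one way in which a Day 7 success is later lost. A denominator without the dead raises the percentage in both arms, and by more in the arm with more deaths.

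**Working it through.** **Arm size.** The illustrations use the planned 104 per arm, so that figure is checked first. Inputs from Protocol 9.1: success rates of 0.80 and 0.60, two-sided alpha 0.05, 88 evaluable per arm, 15% drop-out.

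- Power = Φ[(d√n − z√(2p̄q̄)) / √(p1q1 + p2q2)], with d = 0.20, n = 88, p̄ = 0.70 and z = 1.960.
- Numerator: 0.20 × 9.381 − 1.960 × √0.42 = 1.876 − 1.270 = 0.606. Denominator: √(0.16 + 0.24) = 0.632. Φ(0.958) = 0.831, so the claim of at least 80% holds.
- Drop-out: 88 / 0.85 = 103.5, rounded up to 104 per arm, 208 in total. The plan's figure is reproduced.

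**The two readings.**

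| Question | SAP 4.1 with 17 | SAP 13 |
|---|---|---|
| Missing status at Day 21/33 | Not imputed | As for the primary analysis, if its method includes imputation |
| Death before the visit, no assessment | Can be missing | Category 6, failure |
| Denominator | Not stated; may be subjects with data | ITT |

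The table of planned analyses in SAP 6 includes ITT for additional efficacy. That names the population but does not say how a member without a Day 21 or Day 33 value is counted.

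**Size.** The documents give no planning figure for Day 33 mortality. Their only anchor is the 15% who died in the early 41-patient description in the Protocol introduction. I assume about 5% to 20% per arm. All counts below are assumptions, with every death lacking a visit assessment and no other missing data.

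With x stabilized, d deaths and N = 104, the proportion is x/N if deaths are kept as failures and x/(N − d) if they are dropped.

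| Deaths, Octagam vs placebo | Stabilized | Deaths kept | Deaths dropped |
|---|---|---|---|
| 16 vs 8 | 80 vs 84 | 76.9% vs 80.8%: -3.8 | 80/88 = 90.9% vs 84/96 = 87.5%: +3.4 |
| 21 vs 10 | 73 vs 73 | 70.2% vs 70.2%: 0.0 | 73/83 = 88.0% vs 73/94 = 77.7%: +10.3 |
| 6 vs 16 | 88 vs 76 | 84.6% vs 73.1%: +11.5 | 88/98 = 89.8% vs 76/88 = 86.4%: +3.4 |
| 10 vs 21 | 83 vs 73 | 79.8% vs 70.2%: +9.6 | 83/94 = 88.3% vs 73/83 = 88.0%: +0.3 |
| 5 vs 10 | 83 vs 62 | 79.8% vs 59.6%: +20.2 | 83/99 = 83.8% vs 62/94 = 66.0%: +17.9 |
| 16 vs 16 | 83 vs 62 | 79.8% vs 59.6%: +20.2 | 83/88 = 94.3% vs 62/88 = 70.5%: +23.9 |

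In the first two rows, excess deaths on Octagam turn a small deficit, or no difference, into an apparent benefit. In the next three, fewer deaths on Octagam shrink a real advantage. Equal deaths still change the difference.

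**The case against.** The strongest reply is that category 6 is defined as death, with no limit to any visit, and SAP 12 applies the stabilized-or-improved definition to whichever study day is of interest. Clinical status is scheduled at Days 21 and 33, so a known death could be recorded as 6 with nothing to impute. This stands in part. It rules out the inference that death becomes category 6 only through the Day 7 and Day 14 imputation. It does not close the gap, because SAP 4.1 itself derives the 6 for use where no assessment exists, and no text says that the status form is completed at later visits for a subject who has died.

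Second, other text favours counting deaths. SAP 13 is the ITT primary-endpoint section and is where durability is discussed. SAP 4.1 refers the reader to Sections 12 to 18 for endpoint-specific handling. SAP 1 describes the revised rules as serving clinical status at each visit. The time-to-recovery and time-to-improvement definitions, which run to Day 33, use the primary imputation methods. So a reader may not conclude that the plan excludes deaths; that is one reading of two. But SAP 14 uses the phrase about the primary method with CMH as its example, so method may mean the test and interval alone. SAP 17 also repeats the outputs that the Protocol's durability paragraph requests, which makes it a natural place to implement that comparison.

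Third, a reader might infer that a mortality difference would be hidden. The documents do not support that. Mortality and severe progression through Day 33 are key secondary endpoints, status is tabulated over time, and SAP 4 requires the number with available data, so a reduced denominator would show.

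Finally, the improvement proportion at Days 21 and 33 is an other secondary endpoint, so the no-imputation sentence does not reach it. It merely lacks an explicit rule for those days.

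**Conclusion.** The point holds as a conflict within the SAP. Sections 4.1 and 17 apply no imputation to the Day 21 and Day 33 stabilized-or-improved proportions, Section 13 sends the same comparison to the primary method, and no explicit death-date rule or denominator is written for those days. On the first reading, subjects who died without a visit assessment can drop out.

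Within the assumed mortality range the difference between arms can move by several points in either direction and can change sign. How far depends on the actual death counts and on how many deaths lack a Day 21 or Day 33 record. The consequence is confined to descriptive outputs: neither the Day 7 test nor the hierarchical key secondary tests are touched. It still merits correction before unblinding, because one permitted reading biases the plan's evidence on durability.

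**What to change.** Add one rule to SAP 4.1 and refer to it in SAP 17: for every clinical-status proportion at Days 7, 14, 21 and 33, including the improvement endpoint, a subject who died on or before the visit day has status 6, counts as a failure and stays in the ITT denominator. Saying on or before the visit day also covers a death on Day 7 itself, which the present SAP sentence about earlier deaths does not. Then align SAP 17 with SAP 13 so that a single rule governs the Day 21 and Day 33 output.

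Extending the full carry-forward and ICU-based imputation to Days 21 and 33 is optional; the death rule does not depend on it.

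The cost is a few lines of SAP text. Death dates are already needed for the mortality endpoint. Compared with a survivors-only calculation, the Day 21 and Day 33 percentages fall in any arm with deaths, and the difference between arms may move either way.

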#### **4.2 Analysis Scope of Independent Data Monitoring Committee (IDMC) Meeting and Final Analysis**

The analysis plan for the three scheduled IDMC data reviews can be found in Section 8 of this SAP. The rest of the analysis plan applies to the final analysis that will occur after all subjects have reached Day 33.

#### **4.3 Covariate Adjustment**

Testing will be stratified by age category ( $\leq 65$  versus  $> 65$ ).

#### **4.4 Test Size and Confidence Levels**

Unless otherwise noted, all reported confidence intervals will be computed at the 95% coverage level, and all p-values will be assessed at the two-sided 0.05 significance level. Control for multiplicity is only planned for the analysis of secondary endpoints using a hierarchical testing approach.

#### **4.5 Analysis of Safety Data**

If not further specified, the system organ class (SOC) and preferred term for adverse events analysis will be summarized using Medical Dictionary for Regulatory Activities (MedDRA) Version 23.0 with severity grade defined by CTCAE Version 5.0.

#### **4.6 Reporting Timeframe of Measurement for Analysis**

For analyses of primary and secondary efficacy endpoints, including clinical status and RT-PCR, the latest observation within any given study day will be used. If the observations for the Day 7 visit falls outside of the 24-hour window of the study day or the Day 14 visit falls outside of the 48-hour window of the study day, the observation will be considered as missing and the imputation described in Section 4.1 will apply as appropriate. Otherwise, unless specifically stated otherwise, analyses will be conducted based on nominal visits.

For summary analyses of efficacy assessment, including oxygenation, oxygen saturation, modified Borg Dyspnea Scale and McGill Quality of Life Single-Item Scale (MQoL-SIS) and safety parameters (including vital signs, clinical laboratory evaluations and chest CT/chest X-ray findings), the latest observation within the study day during treatment period will be used. No imputation will be made for these assessments.

For safety analysis with adverse events, the observation with highest severity within the study day during treatment period will be used. No imputation will be made.

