1.2 Benefit-Risk Statement

The risks of IVIG administration are well documented. In general, the incidence of adverse events (AEs) associated with IVIG tends to increase with the rate of infusion, and thus the recommended dosage, infusion rates, and monitoring procedures should

be adhered to. Patients that are naïve to IVIG are more at risk than those that are well-maintained and on regular therapy.

Patients with pre-existing risk factors for thrombotic events (such as advanced age, obesity, hypertension, diabetes mellitus and a history of vascular disease or thrombotic episodes, patients with acquired or inherited thrombophilic disorders, patients with prolonged periods of immobilization, severely hypovolemic patients, and patients with diseases which increase blood viscosity) may be at increased risk of developing thromboembolic events (TEEs) (34). Overdose is possible in overweight and elderly patients and in those who have impaired renal function. In patients with signs of cerebral or cardiac ischemia, the increase in viscosity caused by an immunoglobulin infusion may be a risk (34).

The safety profile of *Octagam 10%* based on clinical studies and long-term post-marketing experience is well-documented and detailed in the European Summary of Product Characteristics (SmPC) (35). Adverse drug reactions (ADRs) such as chills, headache, dizziness, fever, vomiting, allergic reactions, nausea, arthralgia, low blood pressure, and moderate low back pain occur occasionally. These adverse effects are mostly transient and mild. However, some very rare adverse effects, including renal impairment, thrombosis, arrhythmia, aseptic meningitis, hemolytic anemia, and transfusion-related acute lung injury, are serious (36). AEs are rarely disabling or fatal, treatment involves supportive measures, and the majority of affected patients have a good prognosis. Reactions to IVIGs tend to be related to the dose and the rate of infusion. Rarely, human normal immunoglobulins may cause a sudden fall in blood pressure and, in isolated cases, anaphylactic shock, even when the patient has shown no hypersensitivity to previous administration. Cases of reversible aseptic meningitis and rare cases of transient cutaneous reactions have been observed with human normal immunoglobulin. Reversible hemolytic reactions have been observed in patients, especially those with blood groups A, B, and AB.

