5.4 Dose and Dosing Schedule

Octagam 10% is available in glass bottles with different volumes of human immunoglobulin. Glass bottles of different volume should be combined in order to reach the required amount of IgG.

Octagam 10% or placebo will be administered by intravenous infusions on 4 consecutive days. The amount of *Octagam 10%* calculated on the dosage delivery schedule is 2 g/kg divided evenly over 4 days (0.5 g/kg/day).

If a subject is randomized to receive placebo, the same volume with the same infusion rate as would have been applied in case the subject would have been randomized to

2.0 g/kg *Octagam 10%* will be used. Therefore, they will receive an equal dose of placebo given over 4 days.

Body weight is to be measured at Screening or within 24 hours of first IMP administration and reported to the pharmacist or designee as it is needed for the preparation of the following study medication dosages.

All subjects should be clinically assessed for being adequately hydrated prior to IMP administration. TEE prophylaxis should be considered.

The initial infusion rate for each infusion episode will be:

- 0.01 mL/kg/min (60 mg/kg/h) for the first 30 minutes (\pm 5 minutes)
- if tolerated, advanced to 0.02 mL/kg/min (120 mg/kg/h) for the next 30 minutes (\pm 5 minutes)
- if tolerated, advanced to 0.04 mL/kg/min (240 mg/kg/h) for the remainder of the infusion

The interval of 30 minutes may be prolonged as per discretion of the investigator.

In subjects at risk for thromboembolic adverse reactions and acute renal failure (such as advanced age, hypertension, history of thrombotic episodes, subjects with prolonged periods of immobilization, concomitant nephrotoxic medication, diabetes mellitus, overweight, hypovolemia), *Octagam 10%* should be administered at the minimum rate of infusion practicable.

If AEs occur during the infusion, the rate is to be reduced to half the rate at which the event occurred, or the infusion is to be interrupted until symptoms subside. The infusion may then be resumed at a rate tolerated by the subject. In case of severe hypersensitivity or anaphylaxis, the infusion will not be restarted and all treatment with the IMP will be withdrawn. The subject will continue to be followed up in accordance with study-specific procedures as specified in the protocol with the exception that no further administrations of IMP will be performed. The subject will receive ongoing treatment in accordance with local SOC.

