6.1.2 Baseline/Infusion, Visits 1 to 4 (Day 1 to Day 4)

After screening and confirmation of eligibility, subjects will be randomized to receive either placebo or Octagam 10% (blinded). Administration of the first infusion must be started within 1 day (24 hours) after the screening visit. In this acute disease setting, the clinical status of patients can change rapidly. If a patient's eligibility status changes (eg, they require intubation and mechanical ventilation or meet other exclusion criteria) between initial confirmation of eligibility and randomization, they will not be randomized and will be considered a screening failure.

The first infusion of IMP should be initiated as soon as possible after randomization. Eligibility will not be re-assessed again between randomization and dosing. All randomized patients will therefore be dosed irrespective of changes in their clinical condition between randomization and dosing unless the Investigator decides that administration of the IMP would place the patient at additional risk.

The following activities/assessments will be performed **before** the IMP infusion on Day 1:

1. Confirmation of inclusion and exclusion criteria
2. Body weight (if not performed at Screening)
3. Vital signs
4. Physical Examination (if not performed at Screening or available from hospital admission notes, see Section 6.1.1)
5. Confirm medical history
6. Chest CT/Chest X-ray (at Day 1 if not available at Screening, see Section 7.3.6)
7. A-a Gradient (see Section 7.2.4)
8. Clinical Status and Oxygenation/Ventilator Status Evaluation
9. Blood sampling for clinical laboratory evaluations (specified in Section 7.3.4)
10. Randomization

The following activities/assessments will be performed **before** the IMP infusion on Days 2 through 4:

- Vital signs

- Clinical Status and Oxygenation/Ventilator Status Evaluation
- Blood sampling for clinical laboratory evaluations (specified in Section 7.3.4)

All blood sampling (Section 7.3.4) will be done **before** IMP infusion on all dosing days. If the Day 1 infusion commences within 8 hours of the blood collection for the Screening laboratory parameters, only those parameters not assessed at Screening need to be performed prior to the Day 1 infusion. Physical examination and body weight will be performed at Baseline (Day 1) only if it is not performed at Screening.

During and after IMP administration (Day 1 through Day 4):

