The subject will receive either *Octagam 10%* medication in the dose of 2 g/kg administered over 4 days (0.5 g/kg/day), or an equivalent volume of placebo (saline), infused slowly over approximately 2 hours per day over 4 consecutive days. Note: Subjects must be monitored before infusion and carefully observed for any symptoms at least once throughout the infusion period and at least 1 hour thereafter.

The following activities/assessments will be performed on **Day 1 through Day 4**:

1. Infusion of IMP according to randomization code: *Octagam 10%* or placebo
2. Vital signs (taken once during and again after infusion)
3. SpO₂ saturation (see Section 7.2.4)
4. Post-infusion site assessment
5. Modified Borg Dyspnea Scale
6. MQoL-SIS
7. AE monitoring
8. Concomitant medication use review and documentation

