Absolute change in vital signs and clinical laboratory parameters from baseline to each study visit up to Day 33 will be summarized descriptively with mean, standard deviation, median, range and 95% confidence intervals. The clinically significant status of vital signs will also be tabulated.

No missing data will be imputed, and no formal hypothesis testing will be performed for safety endpoints.

Subject level listings of AEs, vital signs, clinical laboratory parameters and inflammation assessment will be provided.

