### **18.3 Analysis of Additional Safety Data**

Descriptive statistics of changes from baseline to each scheduled post-baseline assessment will be provided for vital signs, laboratory test results, and radiological findings. The frequency of drug related reactions will be tabulated by visit. Listings will be provided as well.

For laboratory assessments, the shifts relative to CTCAE criteria for laboratory abnormalities will be provided. The laboratory measures will also be compared with their corresponding normal ranges, and the incidence of abnormally high and abnormally low laboratory values will be summarized.

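### The SAP's latest-of-day rule normally leaves the during-infusion vital signs out of the by-visit safety summaries, so a transient blood-pressure change not reported as an AE could be missed in the comparison between arms

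*SAP*

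**What the plan says.** Protocol 5.4 has the product or placebo "administered by intravenous infusions on 4 consecutive days". Protocol 6.1.2 lists vital signs among the assessments made before the Day 1 infusion, and again among those made before "the IMP infusion on Days 2 through 4". For Days 1 to 4 it adds "Vital signs (taken once during and again after infusion". Each infusion day therefore has three scheduled sets, and Protocol 7.3.5 includes blood pressure in each set.

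SAP 4.6 sets the selection rule for summary analyses. It covers "safety parameters (including vital signs, clinical laboratory evaluations and chest CT/chest X-ray findings", and for these "the latest observation within the study day during treatment period will be used. No imputation will be made for these assessments". The next paragraph of 4.6 treats adverse events differently: there the most severe observation of the day is taken.

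SAP 16 then summarises "Absolute change in vital signs and clinical laboratory parameters from baseline to each study visit up to Day 33". It also plans a table of the clinical significance of vital signs and subject-level listings. SAP 18.3 says that "changes from baseline to each scheduled post-baseline assessment will be provided for vital signs". SAP 4 defines the safety baseline as the last observation before the first dose. No vital-sign table by infusion time point, and none of the most extreme value of the day, is specified.

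**The concern.** Vital signs are a named safety endpoint, and the protocol itself links blood pressure to the product. Section 1 lists raised blood pressure among the side effects of IVIG. Section 1.2 warns: "Rarely, human normal immunoglobulins may cause a sudden fall in blood pressure". Section 1.2 also says that adverse events tend to become more frequent as the infusion rate rises. The reading taken during the infusion is the one scheduled while such a change would be under way, and the SAP's rule normally replaces it with a later value.

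The pre-infusion values on Days 2 to 4 are superseded too. On those days the by-visit table compares a late reading with the value before the first dose on Day 1, so it does not isolate the change across that day's infusion.

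What is at stake is the comparison between arms for short-lived haemodynamic effects. The data are scheduled for collection, but the stated rule keeps much of them out of the planned summaries.

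**Working it through.** The plan gives no figure of its own here, so the check applies the SAP 4.6 rule to the Protocol 6.1.2 schedule and counts vital-sign sets.

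Inputs: 3 scheduled sets per infusion day (before, during, after; Protocol 6.1.2), 4 infusion days (Protocol 5.4), and 208 subjects (Protocol 9.1).

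| Day | Before infusion | During infusion | After infusion, or later that day |
|---|---|---|---|
| 1 | safety baseline (SAP 4) | not used | used |
| 2 to 4 | not used | not used | used |

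1. Scheduled sets per subject: 3 × 4 = 12.
2. Kept by the latest-of-day rule: 1 × 4 = 4.
3. Used as the safety baseline: 1 (Day 1, before infusion).
4. Unused in the by-visit summaries: 12 − 4 − 1 = 7, which is 7/12 = 58%.
5. Make-up of the 7: 4 during-infusion sets and 3 pre-infusion sets (Days 2 to 4).
6. During-infusion sets left out over the whole trial: 4 × 208 = 832.

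The 832 is an upper figure. It requires that every subject has all four infusions, that every during-infusion set is taken, and that each is followed by a later set the same day. If the post-infusion set is missing and nothing later was recorded, the during-infusion set becomes the latest of the day and is kept.

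The remaining question is where a transient change could still be seen:

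- **By-visit change table (SAP 16):** only if the change lasts to the retained reading.
- **AE tables (SAP 16) and drug-related reactions by visit (SAP 18.3):** only if it was reported. Protocol 7.3.2.2 says when an abnormal laboratory value becomes an AE but gives no matching criterion for vital signs, so reporting rests on the investigator's judgement.
- **Clinical-significance table (SAP 16):** unclear, because the SAP does not say whether it draws on all readings or only the latest.
- **Listings (SAP 16):** yes, as far as the text goes. The 4.6 rule governs summaries, and nothing says that listings are cut to one value a day. Listings do not compare the arms, however.

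**The case against.** The strongest reply is that the plan has several other routes to the same information. The post-infusion reading is eligible under 4.6, so a persisting change is summarised. AEs follow a highest-severity rule, drug-related reactions are tabulated, and vital signs are listed. This stands. A reader might infer that infusion-related blood-pressure changes cannot appear at all, or that every during-infusion reading is lost. The documents support neither.

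Second, the baseline rule keeps the Day 1 pre-infusion set in use. A count of 8 unused sets out of 12 (67%) would overlook this. The pre-infusion sets among the 7 also show nothing about that day's infusion on their own; they matter as the reference for same-day change.

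Third, one might argue that values settle because Protocol 5.4 reduces or interrupts the infusion. That step follows an AE, and AEs must be recorded, so this route mostly concerns events already captured. The gap is confined to changes that were not reported as AEs.

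Fourth, it is tempting to say that the tables would show no difference between arms even if infusion-time values differed. This is not shown. The documents time neither the during-infusion nor the post-infusion reading. Under 5.4 the rate is stepped up if tolerated, so the post-infusion reading may follow the fastest phase, while the single during-infusion reading could fall in the slowest one. The supportable statement is that a difference could be missed.

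Finally, SAP 18.3 could be read as covering during-infusion readings, which would remove the omission. But then it contradicts 4.6, which names vital signs explicitly. If 18.3 means visits, the omission remains. On either reading the text needs to be settled.

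**Conclusion.** The point holds in a limited form. With readings taken as scheduled, the by-visit vital-sign summaries leave out all 4 during-infusion sets per subject, up to 832 in the trial, and the 3 pre-infusion sets on Days 2 to 4. That is 7 of 12 sets, or 58%. A blood-pressure change that arises during an infusion, resolves before the last reading of the day and is not reported as an AE could be missing from the planned comparison between arms and visible only in listings.

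The counts assume a complete four-day course, complete readings and a Day 1 pre-infusion baseline. How often such transient, unreported changes would occur cannot be estimated from the documents. Safety analysis here is descriptive, so no hypothesis test or error rate is affected. This is a cheap improvement to the safety reporting, not a threat to the trial's conclusions on efficacy.

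**What to change.** In SAP 4.6, exempt the Day 1 to 4 vital signs from the latest-observation rule. Then:

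- Summarise them descriptively by arm at the pre-, during- and post-infusion time points, as change from that day's pre-infusion value.
- Add the largest rise and the largest fall from the pre-infusion value among the during- and post-infusion readings.
- If a threshold category is shown, count only during- or post-infusion values in subjects who were below the threshold before that infusion. Counting any infusion-day value would include hypertension already present before the dose. Label it a reporting category, not a clinical rule.
- State that the clinical-significance table in SAP 16 uses all readings.
- Align SAP 16 and 18.3 with the revised 4.6.

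The cost is one SAP sentence, the matching wording in 16 and 18.3, and one or two extra descriptive tables. No new measurement is needed.
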